10.7 Physical Examination Data

All physical examination details and comments on any physical examination findings will be listed.

11 Palatability Evaluations

Palatability will be assessed for each test formulation administered in Part 1 (i.e., T1 and T2) using a palatability questionnaire ([Appendix 3](#)), at the time points detailed in [Appendix 1](#). The questionnaire will ask subjects to rate the overall acceptability of palatability, with additional questions asked on specific palatability attributes (e.g., flavour, mouth feel/texture and aftertaste), on a 100 mm VAS scale.

For the purposes of the summaries, acceptability and each palatability attribute will be scored using 0 mm = "I did not like it" through to 100 mm = "I liked it very much" for Questions 1, 3, 4 and 5; 0 mm = "Very gritty/lumpy" through to 100 mm = "Very smooth" for Question 2; 0 mm = "Very difficult" through to 100 mm = "Very easy" for Question 6; 0 mm = "No taste" through to 100 mm = "Very intense taste" for Questions 7 to 11 and 0 mm = "Not at all" through to 100 mm = "Extremely" for Questions 12 to 16.

The safety analysis population will be used for all summary tables described in this section and all randomized subjects will be used for the listings.

11.1 Palatability Evaluations Summary Tables

Palatability data (for all questions on a VAS scale) will be summarized using descriptive statistics (i.e., mean, SD, median, minimum, maximum and n) for each palatability question by test formulation.

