6.6 OTHER ANALYSES

Palatability questionnaire data will be listed and summarized using descriptive statistics.

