11.2 Palatability Evaluations Listings

All palatability data collected (i.e., score for each VAS scale palatability question and comments for all other palatability questions) will be listed.

12 Interim Statistical Analysis

No formal interim statistical analysis is planned for this study.

13 Changes in the Conduct of the Study or Planned Analysis

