14.2.4 Quality Control - Statistical Analysis

QC of statistical analysis will be performed by peer review of program code, log and output. This will be performed by a statistician at Quotient who is not responsible for performing the statistical analysis.

15 SAS Data Transfer

Study data in ADaM dataset format will be transferred to Genentech at the following milestones:

- Pre database close
- Pre database lock
- Post database lock

Data will be provided in SAS dataset format, each dataset will be contained in a respective SAS transport (XPT) file and conform to CDISC ADaM format (SDTM IG 1.1)

The following standards and versions for creation and validation of the Clinical Data Interchange Standards Consortium (CDISC) Standardized Datasets will be used:

- Study Data Tabulation Model (SDTM) Version: 1.4
- SDTM Implementation Guide Version: 3.2
- ADaM: Model 2.1
- Implementation Guide 1.1
- OpenCDISC Version: 2.2.0
- CDISC SDTM Controlled Terminology Version: "2018-06-29 or latest available"
- SDRG (Standard Data Review Guide): 1.2 or latest available
- ADRG (Standard Data Review Guide): 1.1 or latest available
- Define.xml: 2.0> (end of study transfer only)
- SAS v9.4
- Pinnacle 21

A define.xml will be provided to Genentech for ADaM datasets. This will be accompanied by a Data Reviewers Guide (in pdf format) and linked to the ADaM define.xml. Datasets will be provided in SAS transport file format (XPT), each dataset will be in an individual transport file. The define.xml will be issued on finalization of the CSR.

16 Programming Conventions

Quotient standards for layout of tables, figures and data listings and programming conventions will be used as follows:

- courier new, font size 8
- landscape
- US letter size paper

Tables and listings will be produced as MS Word 2013 documents and figures will be produced as PDF files. Listings will be sorted by subject ID number and period.

The mock tables ([Section 21](#)), mock figures ([Section 22](#)) and mock listings ([Section 23](#)) presented are a representation of Quotient reporting standards. However, these are provided for illustrative purposes only. The numbering, titles, formatting, labelling, footnotes and cosmetic appearance of all output may be modified or additional titles, labelling and/or footnotes may need to be added during analysis and reporting, for clarification purposes. Any such changes will not be regarded as changes to planned analysis.

17 Reference List

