14.5.1.2.1	ECGs Summary Statistics: Safety Analysis Population Part 1 <Parameter>
14.5.1.2.2	ECGs QTcF Categorical Data Summary Statistics: Safety Analysis Population Part 1
14.5.1.3	Palatability Evaluations Summary Statistics: Safety Analysis Population <Palatability Question> Part 1

Table Number	Table Title
14.5.2.1	Vital Signs Summary Statistics: Safety Analysis Population Part 2 <Parameter>
14.5.2.2.1	ECGs Summary Statistics: Safety Analysis Population Part 2 <Parameter>
14.5.2.2.2	ECGs QTcF Categorical Data Summary Statistics: Safety Analysis Population Part 2

19 Index of Figures

Figure Number	Figure Title
	Plasma Pharmacokinetic Concentrations and Parameters
14.2.1.1.1	
Plasma Pharmacokinetic Concentrations: Entrectinib Linear/Linear Scale Arithmetic Mean (\pm Arithmetic SD) Values: PK Population Part 1
 
(programming note: all treatments on same plot)
 
(programming note: where concentrations are provided as ng/mL, these will be converted to nmol/L)

14.2.1.1.2	
Plasma Pharmacokinetic Concentrations: M5 Linear/Linear Scale Arithmetic Mean (\pm Arithmetic SD) Values: PK Population Part 1
 
(programming note: all treatments on same plot)
 
(programming note: where concentrations are provided as ng/mL, these will be converted to nmol/L)

14.2.1.1.3	
Plasma Pharmacokinetic Concentrations: Entrectinib and M5 Linear/Linear Scale Arithmetic Mean (\pm Arithmetic SD) Values: PK Population Subtitle: <Treatment> Part 1
 
(programming note: where concentrations are provided as ng/mL, these will be converted to nmol/L)

14.2.1.1.4	
Plasma Pharmacokinetic Concentrations: Entrectinib Linear/Linear Scale Spaghetti Plots of All Individual Values: PK Population Subtitle: <Treatment> Part 1
 
(programming note: where concentrations are provided as ng/mL, these will be converted to nmol/L)

14.2.1.1.5	
Plasma Pharmacokinetic Concentrations: M5 Linear/Linear Scale Spaghetti Plots of All Individual Values: PK Population Subtitle: <Treatment> Part 1
 
(programming note: where concentrations are provided as ng/mL, these will be converted to nmol/L)

Figure Number	Figure Title

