	2 H	xx	xx (xx.x)	xx (xx.x)	xx (xx.x)	xx (xx.x)	xx (xx.x)	xx (xx.x)	xx (xx.x)
	6 H	xx	xx (xx.x)	xx (xx.x)	xx (xx.x)	xx (xx.x)	xx (xx.x)	xx (xx.x)	xx (xx.x)
	48 H	xx	xx (xx.x)	xx (xx.x)	xx (xx.x)	xx (xx.x)	xx (xx.x)	xx (xx.x)	xx (xx.x)
	96 H	xx	xx (xx.x)	xx (xx.x)	xx (xx.x)	xx (xx.x)	xx (xx.x)	xx (xx.x)	xx (xx.x)

Note: The data in this table are presented in listing xx
Each treatment comprised of a 600 mg oral dose of entrectinib administered in the fed state.
BASELINE is defined as Day 1, Pre-dose for each treatment period.
Categories for QTcF interval and QTcF interval increases are based on ICH E14 guidelines.
N# is the total number of subjects in the relevant treatment and is used as the denominator for
the percentages of subjects, n indicates the number of subjects with observations at the given time point.

PROGRAM PATH: X:\~\QSC201525\~\TFLS\PRODUCTION\TAB_XX

DDMMYYYY HH:MM

(Programming note: This table will be continued for all treatments.)
(Programming note: A similar table will be produced for Part 2 ECGs, i.e., Table [14.5.2.2.2]. Treatments
will be 200 mg F06 coarse and 200 mg F06 fine and footnote will state: Each treatment comprised of a 200 mg oral
of entrectinib administered in the fasted state.)

Genentech, Inc.
Protocol: GP41341

Page x of y

TABLE 14.5.1.3
Palatability Evaluations
Summary Statistics: Safety Analysis Population
<Palatability Question>
Part 1

Statistic	600 mg F15 (N=XX)	600 mg F16 (N=XX)	600 mg F06 (N=XX)
	n (%)	n (%)	n (%)
Mean	xx.x	xx.x	xx.x
SD	xx.x	xx.x	xx.x
Median	xx.x	xx.x	xx.x
Min	xx	xx	xx
Max	xx	xx	xx
n	xx	xx	xx

Note: The data in this table are presented in listing xx
Each treatment comprised of a 600 mg oral dose of entrectinib administered in the fed state.
Acceptability and each palatability attribute will be scored using 0 mm = "I did not like it" through
to 100 mm = "I liked it very much".

[figure not shown]
PROGRAM PATH: X:\~\QSC201525\~\TFLS\PRODUCTION\TAB_XX DDMMYYYY HH:MM

(Programming note: A separate page will be used for each palatability question with the relevant subheading.
Footnote on scoring will require to be updated based on question from questionnaire.)

22 Mock Figures

Genentech, Inc.
Protocol: GP41341

FIGURE 14.2.1.1.1
Plasma Pharmacokinetic Concentrations: Entrectinib
Linear/Linear Scale
Arithmetic Mean (\pm Arithmetic SD) Values: PK Population
Part 1

[figure not shown]
Note: Data in the above graph are presented in listing 16.2.5.1.4

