(Programming note: This listing will be continued for all subjects.)
(Programming note: For palatability questions which are not on a VAS scale, the subject's response/comment will be listed.)
(Programming note: Footnote on scoring will require to be updated based on question from questionnaire.)

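### Do the two Yes/No palatability questions need a planned count by formulation?

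*SAP*

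**What the plan says.** Protocol Section 6.6 gives the whole protocol-level plan in one sentence: "Palatability questionnaire data will be listed and summarized using descriptive statistics". It names no items, no statistics and no tables.

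The SAP fills this in. Section 11 defines scoring on a 100 mm scale for Questions 1 to 16 and fixes the analysis set: "The safety analysis population will be used for all summary tables described in this section". Section 11.1 sets the scope of the tables: "Palatability data (for all questions on a VAS scale) will be summarized using descriptive statistics", with mean, SD, median, minimum, maximum and n for each test formulation. Section 11.2 lists everything collected, meaning the score for each visual analogue question and "comments for all other palatability questions". The programming note under mock Listing 16.2.9.1.4 (SAP Section 23) repeats this: "For palatability questions which are not on a VAS scale, the subject's response/comment will be listed".

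The table index (SAP Section 18) has one palatability table, 14.5.1.3, titled "Palatability Evaluations Summary Statistics: Safety Analysis Population". Its mock-up (SAP Section 21) has rows for continuous statistics only, under an n (%) column header, with the note "A separate page will be used for each palatability question with the relevant subheading". SAP Section 16 says of the mock outputs that "these are provided for illustrative purposes only".

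The questionnaire (Appendix 3 of both documents) prints Yes and No boxes for two items: residual bits or lumps after swallowing, and willingness to take the medicine again.

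**The concern.** Read together, these sections leave the two Yes/No items without a planned count for either mini-tablet. The protocol sentence carries no restriction to visual analogue items, and SAP Section 13.2 declares no change to the planned analysis, so the narrower scope goes unmentioned.

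The items matter to the question being asked. The additional objective concerns taste and acceptability. According to Protocol Section 1.2.1, one mini-tablet has a functional taste-masking coating and the other a simple aesthetic one, so a comparison by formulation is what the questionnaire can offer. Willingness to take the product again bears plainly on acceptability. A reader of the study report who wanted the two Yes proportions would find no table giving them. With no count planned in advance, whether one appears in the text could also depend on how the answers fall.

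**Working it through.** The plan states no sample size or precision figure for palatability, so there is nothing to reproduce. The check is mainly a comparison of texts, with a little arithmetic for scale.

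**1. Is there a planned count anywhere?** Section 11.1 covers visual analogue questions. Section 11.2 and the mock-listing note cover the rest by listing. The index has one table, and its mock rows suit a continuous score. SAP Section 14.1 says that categorical data are, as a general rule, shown as counts and percentages. That governs format and does not by itself create a table that Section 11.1 leaves out. The n (%) header in mock Table 14.5.1.3 does not settle the matter either: the same mock shows an F06 capsule column, although the questionnaire is completed only in mini-tablet periods (Schedule of Activities, footnote f), so the header is probably carried over from a template. The factual reading is correct: no count is planned.

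**2. Does that contradict the protocol?** Section 6.6 requires the questionnaire data to be listed and summarized. The SAP lists all items and summarizes the scored ones: 4 (Questions 1, 3, 4, 5) + 1 (Question 2) + 1 (Question 6) + 5 (Questions 7 to 11) + 5 (Questions 12 to 16) = 16 questions. Section 6.6 cannot mean a table for every field, because some fields are free text. The stated endpoint is completion of the questionnaire (Protocol Section 2.3; SAP Section 4.2.3). The SAP specifies a general sentence and does not break it.

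**3. What is lost?** Planned Part 1 enrolment is 15 (Protocol Section 6.1).
- Answers per item: 2 formulations × 15 = 30. Both items: 2 × 30 = 60.
- Protocol Section 4.1 allows up to 19 subjects to be dosed in Part 1. The ceiling is then 2 × 2 × 19 = 76, and fewer in practice, since a replaced subject may not have taken both mini-tablets.
- The 12 in the sample size section is the pharmacokinetic evaluable target. It is not the denominator here, because palatability uses the safety analysis population.

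The mock listing is organized by question and shows subject, period and treatment, so each Yes/No item is about 30 rows on its own pages. SAP Section 15 transfers the data to the sponsor in ADaM format, and SAP Section 3.1 provides for sponsor review of palatability outputs before database lock and of draft outputs after it. A count can be programmed or requested at any of these points.

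**4. How much would the count tell us?** One subject is 100/15 = 6.7 percentage points. The exact (Clopper-Pearson) 95% limits for x Yes answers out of n are the 2.5% quantile of Beta(x, n − x + 1) and the 97.5% quantile of Beta(x + 1, n − x). For assumed counts:

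| Yes / n | Exact 95% interval |
|---|---|
| 7/15 | 21.3% to 73.4% |
| 12/15 | 51.9% to 95.7% |
| 15/15 | 78.2% to 100% |

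Such proportions are descriptive at best.

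**The case for a change.** The best case for a change is that it costs almost nothing: one sentence in Section 11.1, one line in the index and one small table from data already collected. No printed visual analogue question asks about bits remaining after swallowing or about taking the product again, so the tabulated items overlap with the two Yes/No items without replacing them. SAP Section 16 permits modifications to the mock outputs such as titles, formatting and footnotes; it does not mention new summaries. And a count fixed in advance avoids any suspicion of selective reporting.

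Most of this is true, and it supports adding the table as a courtesy. It does not show that the plan goes wrong as written. SAP Section 11 assigns the overall acceptability rating to a visual analogue item, and that item is tabulated. Nothing in the documents ranks willingness to retake above it. Selective reporting has little room when every answer appears in the listing. No test or decision rule uses the palatability data, so a count made later and labelled as additional carries no inferential cost.

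**Conclusion.** The observation is accurate, but no change follows. SAP Section 11.1 is slightly narrower than a broad reading of Protocol Section 6.6, for two items under an additional objective. Following the plan as written gives no wrong or biased result: the 16 scored questions are summarized, and the two Yes/No items are fully listed by subject and treatment. The primary bioavailability analysis and the secondary safety analysis are untouched.

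The gap amounts to two frequency rows per formulation, built from at most 60 answers at planned enrolment (at most 76 if 19 subjects are dosed), where one subject moves a percentage by 6.7 points at n = 15. An analyst writing the palatability section can supply these counts from the listing or datasets and state the number who answered beside each percentage.

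This conclusion rests on two assumptions: that the listing is produced as Section 11.2 describes, and that no formulation choice is tied to the two Yes/No items. The documents mention no such rule.

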Additional	To explore the palatability (taste and acceptability) of coated and uncoated multi-particulate formulations	Completion of palatability questionnaire

Study Design

Description of Study

This is a randomized, open-label, single-center, two-part study in healthy volunteers to explore the performance of entrectinib multi-particulate formulations (Part 1) and the effect of drug substance particle size on entrectinib bioavailability (Part 2).

Part 1

Part 1 is a randomized, open-label, three-treatment, three-period, three-sequence, three-way crossover design. In each treatment period, subjects will receive a single 600 mg oral dose of entrectinib under fed conditions. Entrectinib will be administered as one of three possible formulations:

- Multi-particulate formulation 1: Entrectinib film-coated mini-tablets, 600 mg (240 × 2.5 mg) (Ro 710 2122/F15) (test formulation 1; T1)
- Multi-particulate formulation 2: Entrectinib film-coated mini-tablets, 600 mg (240 × 2.5 mg) (Ro 710 2122/F16) (test formulation 2; T2)
- F06 capsule formulation: Entrectinib (RXDX-101) F06 hard capsules, 3 × 200 mg (Ro 710 2122/F04) (reference formulation; R)

Study treatments will be administered orally within 30 mins of consumption of a standardized light "pediatric" breakfast. The test formulation, provided in a bottle, will be mixed with approximately one tablespoon (~15 mL) of yogurt, which will be swallowed without chewing with approximately 240 mL of water. In each period, palatability (taste and acceptability) of the test formulations will be assessed by completion of a questionnaire shortly after drug administration.

The reference formulation will be dosed as 3 × 200 mg capsules, swallowed whole with approximately 240 mL of water.

A total of 15 subjects will be enrolled. Subjects will be randomly assigned to one of three treatment sequences (i.e., T1T2R, T2RT1, RT1T2) according to a pre-specified randomization scheme based on the order of study enrollment.

Blood samples for measurement of plasma concentrations of entrectinib and its active metabolite M5 will be collected before and at intervals up to 96 hours after study drug dosing in each period.

Entrectinib—Genentech, Inc.

10/Protocol GP41341, Version 1 – 02 April 2019

Safety and tolerability will be monitored by clinical and laboratory assessments at intervals throughout the study.

Part 2

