4.1.3 Additional Objective

The additional objective of the study is:

- to explore the palatability (taste and acceptability) of coated and uncoated multi-particulate formulations (Part 1)

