5.1 Brief Description

This is a randomized, open-label, single-center, two-part study in healthy volunteers to explore the performance of entrectinib multi-particulate formulations (Part 1) and the effect of drug substance particle size on entrectinib bioavailability (Part 2).

Part 1

Part 1 is a randomized, open-label, three-treatment, three-period, three-sequence, three-way crossover design. In each treatment period, subjects will receive a single 600 mg oral dose of entrectinib under fed conditions. Entrectinib will be administered as one of three possible formulations:

- Multi-particulate formulation 1: Entrectinib film-coated mini-tablets, 600 mg (240 x 2.5 mg) (Ro 710-2122/F15) (test formulation 1; T1)
- Multi-particulate formulation 2: Entrectinib film-coated mini-tablets, 600 mg (240 x 2.5 mg) (Ro 710-2122/F16) (test formulation 2; T2)
- F06 capsule formulation: Entrectinib (RXDX-101) F06 hard capsules, 3 x 200 mg (Ro 710-2122/F04) (reference formulation; R)

Study treatments will be administered orally within 30 min of consumption of a standardized light "pediatric" breakfast. The composition of the "pediatric" breakfast is as follows:

- 1 hard-boiled egg
- 2 slices of wholemeal bread
- Fruit (e.g., strawberry) jam

The test formulation, provided in a bottle, will be mixed with approximately one tablespoon (~15 mL) of yogurt, which will be swallowed without chewing with approximately 240 mL of water. In each period, palatability (taste and acceptability) of the test formulations will be assessed by completion of a questionnaire shortly after drug administration ([Appendix 3](#)).

The reference formulation will be dosed as 3 × 200 mg capsules, swallowed whole with approximately 240 mL of water.

[figure not shown]
The total duration of the study for each enrolled subject (screening through to end of study) will be up to 10 weeks, divided as follows:

- screening: up to 28 days before the first dose of study drug
- three treatment periods, separated by a treatment-free washout so that there are at least 14 days between each of the three study drug administrations
- safety follow-up phone call: 12 to 14 days after the last dose of study drug

Subjects will be resident in the clinic from the morning of Day -1 until at least Day 3 in each treatment period. Subjects will also have ambulatory clinic visits at screening, and Days 4 and 5 in each treatment period.

[Figure 1](#) presents an overview of the study design.

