5.2 Study Sample Size

It is planned that a total of 15 subjects will be enrolled in Part 1 and 16 subjects will be enrolled in Part 2 of the study to achieve 12 evaluable subjects in each part. Subjects who withdraw from the study may be replaced at the discretion of the Sponsor and principal investigator (PI) to ensure that in each part, 12 subjects complete the study and have evaluable PK data from all treatment periods.

The sample size has been chosen to ensure that the ratios of the geometric means for the PK parameters of entrectinib can be estimated with sufficient precision. In a previous study (Study RXDX-101-15), the within-subject coefficients of variation for $AUC_{0-\infty}$ and C_{max} following administration of a single dose of entrectinib were estimated

to be 20% and 16%, respectively. Based on a coefficient of variation of 20%, with 12 evaluable subjects it is estimated that the lower and upper bounds of the 90% CIs of the ratio will be within 1.25x of the corresponding point estimates for each of the two entrectinib PK parameters ($AUC_{0-\infty}$ and C_{max}).

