5.3 Randomization (Including Replacement Subjects)

Part 1

Using a computer-generated randomization schedule, subject numbers will be allocated to one of three treatment sequences ([Table 2](#)) in Part 1. The allocation will be balanced with 5 subjects assigned to each of the treatment sequences.

Table 2 Part 1 Treatment Sequences

Treatment Sequence	Period 1	Period 2	Period 3
T1T2R	Test formulation 1	Test formulation 2	Reference formulation
T2RT1	Test formulation 2	Reference formulation	Test formulation 1
RT1T2	Reference formulation	Test formulation 1	Test formulation 2

T1; Test formulation 1 = Multi-particulate formulation 1: Entrectinib film-coated mini-tablets, 600 mg (240 x 2.5 mg) (Ro 710-2122/F15)

T2; Test formulation 2 = Multi-particulate formulation 2: Entrectinib film-coated mini-tablets, 600 mg (240 x 2.5 mg) (Ro 710-2122/F16)

R; reference formulation = F06 capsule formulation: Entrectinib (RXDX-101) F06 hard capsules, 600 mg (3 x 200 mg) (Ro 710-2122/F04)

Eligible subjects will be assigned a unique identification number on the morning of dosing in Period 1 according to the code █ to █ for Part 1, using the lowest number available. Replacement subjects will be allocated subject numbers █ to █, where the last 2 digits are the same as those of the original subject (e.g., if Subject █ withdraws the replacement will have Subject Number █). Replacement subjects will be assigned to the same treatment sequence as the subject they replaced.

A treatment allocation list will be produced prior to dosing using the randomization schedule and will be retained in the Investigator Site File (ISF).

The original randomization schedule and proof of quality control procedures will be held by the Data Sciences department at Quotient Sciences until the study is archived, at which time the randomization materials will be retained in the ISF.

Part 2

Using a computer-generated randomization schedule, subject numbers will be allocated to a treatment sequence ([Table 3](#)) in a 1:1 ratio in Part 2. The allocation will be balanced with 8 subjects assigned to each treatment sequence.

Table 3 Part 2 Treatment Sequences

Treatment Sequence	Period 1	Period 2
TR	Test formulation	Reference formulation
RT	Reference formulation	Test formulation

T = Test formulation; Entrectinib F06 HPMC Capsules (coarse API), 200 mg

R = Reference formulation; Entrectinib (RXDX-101) F06 hard capsules, 200 mg (fine API) (Ro 710-2122/F04)

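### Palatability is tabulated by formulation while tasting order is imbalanced 2:1; a within-subject, order-balanced F15 minus F16 difference would be a cheap, minor improvement

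*SAP*

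**What the plan says.** The palatability aim is an additional objective in both documents; SAP 4.1.3 words it as "to explore the palatability (taste and acceptability) of coated and uncoated multi-particulate formulations (Part 1"). The associated endpoint (SAP 4.2.3, Protocol 2.3) is simply that the questionnaire is completed. Protocol 1.2.1 explains that one mini-tablet product has a taste-masking coat and the other a cosmetic one.

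SAP section 11 limits the ratings to the two test products: "Palatability will be assessed for each test formulation administered in Part 1 (i.e., T1 and T2"). The items are scored on a 100 mm VAS. SAP 11.1 then gives n, mean, SD, median and range "for each palatability question by test formulation". Mock Table 14.5.1.3 sets the formulations in adjacent columns, with no difference column and no split by order. The population is the safety population, that is, anyone who took at least one dose. Protocol 6.6 also promises only listings and descriptive summaries.

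On the design, SAP 5.2 plans that "a total of 15 subjects will be enrolled in Part 1", and SAP 5.3 adds: "The allocation will be balanced with 5 subjects assigned to each of the treatment sequences". The sequences are T1T2R, T2RT1 and RT1T2, where T1 is F15, T2 is F16 and R is the capsule.

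**The concern.** The three sequences form a Latin square, so each formulation appears once in each period. That balance concerns three treatments, and only two of them are tasted as mini-tablets in yogurt. Remove the capsule and the order of the two tastings is F15 then F16 in two sequences, and F16 then F15 in one. If a second tasting is scored differently from a first one, through familiarity or expectation, part of that shift shows up as a difference between products. The study is open-label, and Protocol 1.1.2.1 lists altered taste and oral sensory symptoms among the commonest events in healthy subjects, so such a shift is plausible. The documents do not show that it exists or how large it would be.

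There is a second, smaller issue. A subject who withdraws after tasting only one product still contributes to that product's column. The difference between columns then mixes within-subject and between-subject information.

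What is at stake is modest: an informal reading of which mini-tablet was better liked.

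**Working it through.** **Inputs.** 15 subjects in Part 1 (SAP 5.2); 5 per sequence and the three sequences (SAP 5.3); T1 = F15 and T2 = F16 (SAP 5.1); only T1 and T2 rated (SAP 11); doses at least 14 days apart (SAP 5.1). Neither document gives an order effect, an SD or a within-subject correlation for palatability, so those are assumptions.

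**The plan's own figure.** 3 sequences × 5 subjects = 15, which reproduces the stated enrolment. No precision figure is stated for palatability; the sample size rests on pharmacokinetic precision.

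**Tasting order.**

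| Sequence | n | F15 period | F16 period | Tasted first | Minimum gap |
|---|---|---|---|---|---|
| T1T2R | 5 | 1 | 2 | F15 | 14 days |
| T2RT1 | 5 | 3 | 1 | F16 | 28 days |
| RT1T2 | 5 | 2 | 3 | F15 | 14 days |

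F15 is first for 5 + 5 = 10 subjects and F16 for 5. Mean period is (1 + 3 + 2)/3 = 2 for F15 and (2 + 1 + 3)/3 = 2 for F16, so calendar period is balanced.

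**Effect on the difference of column means.** Let δ be the true F15 minus F16 difference and let a second tasting score d mm higher than a first, whichever product it is. The expected within-subject difference is δ − d when F15 is first and δ + d when F16 is first. With complete data the difference of column means is

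[10(δ − d) + 5(δ + d)]/15 = δ − d/3.

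The bias has size d/3: 5/3 = 1.7 mm, 10/3 = 3.3 mm and 20/3 = 6.7 mm for assumed d = 5, 10 and 20 mm.

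**If only 12 subjects rate both.** The share of d that enters is (F15-first minus F16-first)/12. It is (8 − 4)/12 = 0.33 if the 2:1 split is kept, (7 − 5)/12 = 0.17 at 7:5, and (10 − 2)/12 = 0.67 at 10:2.

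**Period adjustment does not help.** Three sequences supply three mean within-subject differences. Formulation and two period contrasts use up all three, and with d = 10 mm that model still misstates the formulation effect by 3.33 mm. A tasting-order term cannot be estimated alongside a full period term (rank 3 for 4 parameters). Formulation and order without period can be estimated.

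**Equal weighting of the two orders.** [(δ − d) + (δ + d)]/2 = δ, so the bias from d is zero. Relative to the raw paired mean, the standard error is √[0.25(1/10 + 1/5)] / √(1/15) = √0.075 / √0.0667 = 1.061.

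**Limit of that remedy.** If the shift is d1 when F16 is second and d2 when F15 is second, the average becomes [(δ − d1) + (δ + d2)]/2 = δ − (d1 − d2)/2. It is unbiased only when d1 = d2.

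**The case against.** The strongest reply is that the SAP delivers what it promises. The objective is additional and exploratory, the endpoint is questionnaire completion, and Protocol 6.6 asks only for description. The treatment comparisons named in SAP 9.2.4 for Part 1 are each test product against the capsule; F15 against F16 is not named anywhere. No test or decision threshold exists for a bias to distort, and a bias of 1.7 to 3.3 mm is small on a 100 mm scale. All of this stands, and it is why the point is minor.

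Three stronger readings are tempting, and the documents do not support them.

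- A reader might infer that formulation is wholly confounded with order. It is not: both orders occur, period is balanced and only a third of an additive order effect enters.
- A reader might infer that a planned F15 versus F16 contrast is biased. None is planned; the contrast is one that readers would draw for themselves.
- A reader might infer that ignoring the pairing distorts the result. With complete pairs, the difference of the two means equals the mean paired difference. Pairing then affects only precision: the unpaired standard error is 1.20, 1.41 or 1.83 times the paired one at assumed correlations of 0.3, 0.5 or 0.7. The SAP computes no such standard error. Pairs and order can also be rebuilt from Listing 16.2.9.1.4, which shows subject, period and treatment.

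What the reply does not remove is that descriptive means carry bias as readily as tested ones. With two products that differ in their coat placed in adjacent columns, a reader will compare them.

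**Conclusion.** The point holds as a minor, inexpensive improvement to an exploratory summary, not as an error against the stated objective. The 10:5 split and the absence of any within-subject or by-order summary follow directly from the documents. The d/3 share assumes complete data at the planned allocation and an additive second-tasting effect that is the same for both products. The size in millimetres depends entirely on the assumed d. The documents do not say which of F15 and F16 has the taste-masking coat, nor whether a second tasting would score higher or lower, so they do not show which coat any bias would favour. The loss of the within-subject character of the column difference arises only if some subjects rate one product and not the other. The plan allows for this by enrolling 15 to obtain 12 evaluable and by using the safety population.

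**What to change.** Keep the SAP 11.1 table as planned. Add one table per VAS item, restricted to subjects who rated both products, giving the within-subject F15 minus F16 difference (n, mean, SD and, descriptively, a confidence interval):

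- for F15-first subjects (T1T2R and RT1T2);
- for F16-first subjects (T2RT1);
- as the equal-weight average of the two orders.

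State that the intervals are descriptive. SAP 11 lists up to 16 VAS items, and one order has only 5 planned subjects.

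The cost is a short SAP addition and some programming, with no new data. The equal-weight average has a standard error about 6% larger than the raw paired mean at a 10:5 split. It removes only an order effect common to both orders, so the by-order rows should be shown alongside it.
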